Patients in whom dose increase was made	
Patients in whom 160 mg/2 weeks was administered as the initial dose, 80 mg/2 weeks as the second dose, 40 mg/2 weeks as the third and subsequent dose, and 160 mg or 80 mg was administered at least once thereafter are applicable.

Administration status (total number of administrations, dose)	
 
The number of administrations 
 
[1] Data should be sorted by the start date of the treatment, separate volume, and the number of the cycle of treatment described in “Administration status of this drug” in that order.
 
[2] Administration intervals should be calculated by administration status.
 
 
 
The administration interval should be 14 days for the initial and second administration.
 
The third and subsequent administration should be given according to following rules.
 
If there is a check mark in “once/2 weeks” box, the administration intervals should be 14 days, and in any other situations, a data should be obtained from “[HUMIRA BD] converted data to be provided for analysis”.
 
[3] The number of administrations by administration status should be calculated.
 
The number of administrations = (The last date of the administration (after complement) - the start date of the administration (after complement))/the administration intervals (days)
 
[4] Result obtained according to [3] is larger than 0 and smaller than 1, the number of administrations should be 1.
 
In addition, that number is 1 or larger, the number of administrations should be obtained by rounding off the decimal point.
 
[5] The number of administrations should be sum total of [4] by patients
 
 
Dose 
 
[1] If the dose of this drug is classified as other, the data should be obtained from “[HUMIRA BD] converted data to be provided for analysis”.
 
[2] The dose by administration status should be calculated.
 
 
 
The dose = The number of administrations × the dose
 
[3] Total dose should be sum total of [2] by patients
 
 
Mean daily dose 
 
Mean dose = Total dose/Total number of administrations
 
 
 
 

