## 11. Method of dividing hierarchy of data

data	Method of dividing hierarchy
Dosage and administration	160mg→80mg→40mg/2 weeks, no changes thereafter 160mg→80mg→40mg/2 weeks, and 160mg or 80mg is administered at least once thereafter 160mg, and not administered thereafter 160mg→80mg, and not administered thereafter 80mg, and not administered thereafter 40mg, and not administered thereafter others
the number of administrations	at least once and less than 4 times at least 4 times and less than 12 times at least 12 times and less than 26 times at least 26 times and less than 39 times at least 39 times and less than 52 times at least 52 times and less than 65 times at least 65 times and less than 78 times at least 78 times
Total dose	lower than 500mg at least 500mg and lower than 1000mg at least 1000mg and lower than 2000mg, at least 2000mg and lower than 3000mg at least 3000mg unknown
Mean daily dose	lower than 40 mg at least 40 mg and lower than 60 mg at least 60 mg and lower than 80 mg at least 80 mg and lower than 100 mg at least 100 mg unknown

data	Method of dividing hierarchy
Administration duration	at least 0 week and shorter than 4 weeks (1-28 days) at least 4 week and shorter than 12 weeks (29-84 days) at least 12 weeks and shorter than 24 weeks (85-168 days) at least 24 weeks and shorter than 52 weeks (169-364 days) at least 52 weeks and shorter than 104 weeks (365-728 days) at least 104 week and shorter than 156 weeks (729-1093 days) unknown * When the start date of the administration is defined as 1
Reasons for discontinuation	Occurrence of adverse events, insufficient effect, patient's request, not visiting, others, multiple reasons, unknown, and not described
Sex	male, female, unknown, not described
Pregnancy/lactation	Without pregnancy/lactation, during pregnancy, during lactation, unknown, not described
Race	Japanese, other Asians, others, unknown, not described
Age (years)	Younger than 15 years, 15 years or older and younger than 65 years, 65 years or older, unknown/not described
Body weight (kg)	Lower than 30, 30 or higher and lower than 40, 40 or higher and lower than 50m, 50 or higher and lower than 60, 60 or higher, unknown/not described
Body height (cm)	Lower than 140, 140 or higher and lower than 150, 150 or higher and lower than 160, 160 or higher and lower than 170, 170 or higher and lower than 180, 180 or higher and lower than 190, 190 or higher, unknown/not described

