## efficacy analysis

Objective of analysis: Distribution of the number of administration, total dose, mean daily dose, days to last date of administration are shown

Analysis items: For the number of administration, total dose, and mean daily dose, the number of patients according to the classifications defined in “11 method of dividing hierarchy of data” and rate of the patients to those included in analysis should be calculated. In addition, summary statistics should be calculated for each measurement. Day to the last date of administration should be calculated according to “days to last date of the final administration of this drug” in “10.1 Overall”, and the number of patients by Time Allowance containing corresponding to days of administration in each patient defined in “12.1 time of evaluation of administration status of this drug” and rate of the patients to those included in analysis should be calculated. Summary of statistics of days of administration should be calculated.

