Company should be displayed as name Name of prefecture should be obtained from “Nippon Ultmarc Inc. classification of reassessment”

(5) Abbreviated name of patients

According to GB, “Not applicable” should be used

(6) Sex

According to GB, description should be as male, female, unknown, or not described

(7) Birth date (or age)

Description should be unified to age. According to GB, description should be as ”A + age + "0000""

(8) Distinction between inpatient and outpatient

According to GB, description should be as inpatient, outpatient, unknown, or not described.

(9) Reasons for use

Code, disease name: LLT code and name displayed as LLT of MedDRA should be obtained based on reason for use of this drug described in the survey sheet

(10) Severity before administration

“items not collected” should be applied.

(11) Complications

Presence or absence: “presence or absence of complications” defined in “10.1

Overall”.

The number of complications described: The number of PT codes applied to the complications based on MedDRA should be employed. Complication with the same PT code in one patient should be counted as 1. If there is no complication, “0” should be applied.

Name of complication: It should represent a name of PT based on MedDRA Description should include detailed classification of complications, disease name as complication, and consecutive number of complications in that order. This item should be left as blank space if the number of complication described is “0”.

(12) Administration route

“SC” should be employed.

(13) The maximum dose (daily dose/one time dose)

The one time maximum dose should be employed. According to “Administration status (dosage and administration)” defined in “10.1 Overall”, the maximum value by patients should be employed.

(14) Mean dose (daily dose/one time dose)

Mean one time dose should be employed.

According to “Administration status (total number of administration, total dose)” defined in “10.1 Overall”, “total number of administration/total dose” should be employed.

(15) unit

“MG” should be employed.

(16) The number of administrations per day (the maximum)

“1” should be applied.

(17) Duration of use

According to “Administration status (total number of administration, total dose)” defined in “10.1 Overall”, value for “total number of administration” should be employed.

(18) Concomitant drug

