**“2.9 Incidence of adverse reactions (serious adverse reaction and adverse reaction) by patient characteristics”**

Patients included in analysis: Patients included in safety analysis

Objective of analysis: Incidence of adverse reactions should be shown by patient characteristics and factor analysis should be conducted.

Analysis items: In patients in whom adverse reactions occurred in the period subject to safety analysis, the number of all the patients, the number of patients with serious adverse reactions, and rate of these patients to those included in analysis, the number of the patients with adverse reactions and rate of these patients to those included in analysis, and test provided for the adverse reactions (Fisher’s exact test for nominal scale factors, and Mann-Whitney u test for ordinal scale factors) should be calculated by following patient characteristics:

Notes: Patient characteristics are as follows: Age (years), sex, disease duration (years), complication, hepatic function disorder as complication, renal impairment as complication, medical history, allergy history, smoking habit, self-administration as administration status of this drug, previously used drug/previous treatment, biological preparation adalimumab as previously used drug, biological preparation infliximab as previously used drug, steroid as previously used drug, immunomodulative drug as previously used drug, immunosuppressive drug as previously used drug, oral adrenocortical steroid as concomitant drug, oral mucosa recurrent aphthous ulcer as main symptoms of Behcet disease other than gastrointestinal symptoms, cutaneous symptoms as main symptoms of Behcet disease other than gastrointestinal symptoms, eye symptoms as main symptoms of Behcet disease other than gastrointestinal symptoms, ulcer of vulva as main symptoms of Behcet disease other than gastrointestinal symptoms, arthritis without deformity or rigidity as accessory symptoms of Behcet disease other than gastrointestinal symptoms, epididymitis as accessory symptoms of Behcet disease other than gastrointestinal symptoms, vascular lesion as accessory symptoms of Behcet disease other than gastrointestinal symptoms, moderate or higher degree central nervous lesion as accessory symptoms of Behcet disease other than gastrointestinal symptoms, diagnostic classification of Behcet disease, days until the last date of the administration, and mean daily dose.

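### SAP Table 2.3, item (14) inverts the mean one-time dose: it divides the number of administrations by the total dose, contrary to Section 10.1 and the MG unit

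*SAP*

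**What the plan says.** Item (14) of Table 2.3 in SAP Section 13.2 sets the content of a mean dose field. It first fixes the quantity: "Mean one time dose should be employed". It then points to the Section 10.1 entry on administration status, whose title it gives as "total number of administration, total dose", and closes with the expression to be output: "total number of administration/total dose” should be employed". Item (15) fixes the unit: "MG” should be employed".

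The Section 10.1 entry builds the total dose as the sum, over a patient's records, of the number of administrations times the dose. It then gives the only derivation of a mean dose in the plan: "Mean dose = Total dose/Total number of administrations". Section 11 bands that mean in mg, for example "at least 40 mg and lower than 60 mg".

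Table 2.3 covers all patients whose survey sheet data were fixed. Section 3.1 says that some or all of the results will support the report to the authority and the reassessment application.

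**The concern.** Item (14) and the entry it cites state the same ratio with numerator and denominator exchanged. Only the Section 10.1 version is a dose per administration. The item (14) version is a count per mg placed under an MG label.

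What is at stake is one dose column in a regulatory patient listing. A programmer who follows the item (14) text literally would fill that column with values that are not doses and that rank patients in reverse: the patient with the highest mean dose would show the lowest figure.

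**Working it through.** **Inputs**

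- Quantity wanted: mean dose per single administration (Table 2.3, item 14).
- Unit: mg (Table 2.3, item 15).
- Total dose *T*: sum over records of number of administrations × dose in mg (Section 10.1).
- Number of administrations *N*: sum over records (Section 10.1).
- Regimen for the example: 160 mg, 80 mg, then 40 mg every 2 weeks (Sections 10.1 and 11).
- Assumption for the example: full two-weekly dosing, each injection counted once.

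**Units**

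- Section 10.1: *T*/*N* is in mg per administration, which is a one-time dose.
- Item (14) as written: *N*/*T* is in administrations per mg, which is not a dose.

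**Numbers**

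| Injections *N* | Total dose *T* (mg) | Section 10.1, *T*/*N* (mg) | Item (14), *N*/*T* (per mg) |
|---|---|---|---|
| 1 | 160 | 160 | 0.0063 |
| 2 | 160 + 80 = 240 | 120 | 0.0083 |
| 3 | 240 + 40 = 280 | 93.3 | 0.0107 |
| 26 (52 weeks) | 240 + 24 × 40 = 1200 | 46.15 | 0.0217 |
| 52 (104 weeks) | 240 + 50 × 40 = 2240 | 43.08 | 0.0232 |
| 78 (156 weeks) | 240 + 76 × 40 = 3280 | 42.05 | 0.0238 |

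The correct value exceeds the written one by a factor of (*T*/*N*)². At 52 weeks this is 46.15² ≈ 2130.

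**Ranking.** Take a 52-week patient raised to 80 mg after five 40 mg doses: *T* = 160 + 80 + 5 × 40 + 19 × 80 = 1960 mg and *N* = 26. The mean is 75.38 mg, above the 46.15 mg of the unescalated patient. Item (14) would give 26/1960 = 0.0133, below that patient's 0.0217.

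**Sensitivity to the counting rule.** Section 10.1 sets the last date of the first and second treatments equal to their start date, so (last − start)/14 = 0 for both. Its rounding step raises only results above 0 to 1. Read literally, these two records contribute nothing. At 52 weeks that leaves *N* = 24 and *T* = 24 × 40 = 960 mg, so *T*/*N* = 40.0 mg and *N*/*T* = 0.0250. A patient with only one or two doses would then have 0/0 and no mean under either formula. The counting rule therefore changes the example values, but the inversion remains.

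**Is the slash a separator?** If it were, item (14) would call for two totals where one mean is required, and would repeat the administration count that item (17) already takes from the same Section 10.1 entry. Section 10.1 itself uses the slash for division, both in its administration count and in its mean dose.

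**Reach.** Table 1.6 tabulates the mean through Section 11 ("For the number of administration, total dose, and mean daily dose"). Table 2.9 lists it as a factor ("days until the last date of the administration, and mean daily dose"), and Table 3.4 does the same. All three rest on Section 10.1 and none draws on item (14).

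**The case against.** The strongest reply is that the plan corrects itself. Item (14) cites Section 10.1, names the quantity as a mean one-time dose and is followed by an MG unit. All three point to total dose over number, so the intended value can be recovered from the plan alone. The phrase repeats the two terms of the cited entry's title in the same order, and the plan often uses a slash as a separator, including in item (14)'s own heading. It may be a loose label or a translation slip. A figure near 0.02 would also sit beside item (13), the maximum one-time dose, which is 160 mg on the standard regimen, so review would very likely catch it. Finally, the 1- to 3-dose figures depend on counting each injection once.

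Much of this stands, and it limits the consequence. The intent is recoverable, wrong output would be conspicuous, and the short-course figures are conditional on the counting assumption. It does not make the text right. Read as division, the formula is inverted. Read as a separator, item (14) has no expression of its own for the mean. The line needs correcting either way, and a derivation rule should not rely on the programmer overriding it.

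**Conclusion.** The concern holds. Item (14) states the reciprocal of the Section 10.1 mean dose and is incompatible with the unit in item (15). Programmed as written, the column would show about 0.006 to 0.024 in place of about 160 down to 42 mg on the standard regimen, with each injection counted once. Under the literal Section 10.1 count, the 52-week case is 0.0250 in place of 40.0 mg. These values are illustrative and rest on full two-weekly dosing; the inversion itself rests on no assumption.

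The effect is limited to one column of one patient listing, with no bearing on any test, incidence or efficacy rate. It should be corrected because the listing is regulatory material and every calculable value in the column would be wrong.

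**What to change.** In Table 2.3, item (14), replace the quotient with total dose divided by total number of administrations, identical to the Section 10.1 formula, and keep MG as the unit in item (15). If the listing has already been programmed, check that the column follows the Section 10.1 formula.

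The cost is one line of SAP wording and one line of code. No new data are needed and no other table changes.

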#### “2.4.1 List of occurrence status of events defined as primary survey item”

Patients included in analysis: Patients included in safety analysis

Objective of analysis: In adverse events that occurred in the period subject to safety analysis, summary statistics of days to onset of the events, the number of patients by the outcome, and days to outcome (Resolved or resolving) is shown.

Analysis items: The number of patients in whom the events occurred and rate of these patients to those included in analysis and the number of patients with serious adverse events and rate of these patients included in analysis by types of adverse events (primary survey item and PT) that occurred in the period subject to safety analysis should be calculated. In addition, summary of statistics (the number of patients, the mean, median, maximum values) of days to onset of adverse events by PT and primary survey items (the number of PT code), the number of patients by outcome, summary of statistics of days from onset to outcome (Resolved or resolving) (the number of patients, the mean, median, minimum, and maximum values) should be calculated.

Notes: If there are events with the same PT in one patient, days to onset, outcome, and days to outcome (Resolved or resolving) should be aggregated as 1 event (1 patient) according to following rules.

- Priority for seriousness: Serious > non-serious
- Days to onset: It is identified based on the description in 10.2 days from start date of the initial administration of this drug to onset of adverse event.
- Outcome: It is identified based on the description as outcome in 10.2.
- Days to outcome (Resolved or resolving): It is identified based on the description in 10.2 days from onset of adverse event to outcome (Resolved or resolving).

#### “2.4.2 List of occurrence status of events defined as primary survey item (adverse reaction)”

Patients included in analysis: Patients included in safety analysis

Objective of analysis: In adverse reactions that occurred in the period subject to safety analysis, summary statistics of days to onset of the reactions, the number of patients by the outcome, and days to outcome (Resolved or resolving) is shown.

Analysis items: The number of patients in whom adverse reactions occurred and rate of these patients to those included in safety analysis, the number of patients in whom serious adverse reactions occurred and rate of these patients to those included in

analysis by types of the adverse reactions in the period subject to safety analysis should be calculated. In addition, summary of statistics (the number of patients, the mean, median, maximum values) of days to onset of adverse events by PT and primary survey items (the number of PT code), the number of patients by outcome, summary of statistics of days from onset to outcome (Resolved or resolving) (the number of patients, the mean, median, minimum, and maximum values) should be calculated.

Notes: If there are events with same PT in one patient, “2.4.1 List of occurrence status of primary items” should be referred to.

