Adverse reactions that occurred during the period subject to safety analysis	Among adverse events that occurred during the period subject to safety analysis, those for which causal relationship with this drug cannot be ruled out should be included
Adverse reactions that occurred outside the	Among adverse events that occurred outside the specified safety analysis period, those for which causal relationship with this drug

Terms and abbreviations	Definition
specified safety analysis period	cannot be ruled out should be included
Summary statistics	The number of patients, mean value, standard deviation, the minimum value, the first quartile point, median value, the third quartile point, and the maximum value should be applicable
MedDRA/J	Medical Dictionary for Regulatory Activities / Japanese edition(ICH MedDRA/J)
SOC	System Organ class in MedDRA/J
PT	Preferred Term in MedDRA/J
LLT	lower Level Term in MedDRA/J
IGRA test	Interferon $\gamma$ free release test
GB	Green Book Guidance for application for reassessment

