Serious adverse reactions	
Of adverse events, those assessed as serious using seriousness criteria for company's seriousness assessment described in "Humira BD_AE matching list (reassessment) (after linking)_20170110" are deemed as serious adverse reactions.
 
Serious adverse reactions occurred: At least one record of serious adverse reaction is found.
 
Serious adverse reactions did not occur: Other than above
 
The same counting method as that for adverse events shall be used for the number of serious adverse reaction.

Outcome	
When adverse event, adverse reaction, serious adverse event, and serious adverse reaction are aggregated by outcome, if multiple events with same SOC or those with same PT were present in 1 patient, such events should be identified using outcome in company's outcome assessment described in "Humira BD_AE matching list (reassessment) (after linking)_20170110" according to the priority as follows:
 
[1] Death [2] Sequela [3] Not resolved [4] Unknown [5] Not described [6] Resolving [7] Resolved

Days from the start date of the initial administration of this drug until the onset date of adverse event	
Onset date described in company's assessment in "HumiraBD_AE matching list (for reassessment) (after linking)_20170110" should be used. Derivation can be executed if the start date of the initial administration of this drug and onset date of adverse event is identified with complete date.
 
If the start date of the initial administration of this drug is the same as or earlier than the onset date of the adverse events:
 
The onset date of adverse event - the start date of the initial administration of this drug + 1

Name of data	Derivation and calculation method
	
The start date of the initial administration of this drug is later than the onset date of adverse event:
 
The onset date of adverse event - the start date of the initial administration of this drug
 
If there are multiple events with same PT in 1 patient, the onset date of the event that occurred first should be used to identify the events to be aggregated.

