#### “2.4.3 List of occurrence status of adverse reactions (Important identified risk)”

Patients included in analysis: Patients included in safety analysis

Objective of analysis: In adverse reactions that occurred in the period subject to safety analysis, summary statistics of days to onset of important identified risks, the number of patients by the outcome, and days to outcome (Resolved or resolving) is shown.

Analysis items: The number of patients in whom adverse reactions occurred and rate of these patients to those included in analysis, the number of patients in whom serious adverse reactions occurred and rate of these patients to those included in analysis by types of important identified risks (important identified risk, PT) in the period subject to safety analysis should be calculated. In addition, summary of statistics of days to onset of adverse reactions (the number of patients, the mean, median, maximum values), the number of patients by outcome, summary of statistics of days from onset to outcome (Resolved or resolving) (the number of patients, the mean, median, minimum, and maximum values) by PT and important identified risks (total number of PT code) should be calculated.

Notes: If there are events with same PT in one patient, “2.4.1 List of occurrence status of primary items” should be referred to.

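### Table 2.4.2 covers adverse reactions but specifies onset times for adverse events, and Tables 2.4.2 and 2.4.3 do not say that causality is filtered before repeated PTs are collapsed

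*SAP*

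**What the plan says.** Table 2.4.2 (SAP 13.2) states its scope in the objective: "In adverse reactions that occurred in the period subject to safety analysis, summary statistics of days to onset of the reactions". Its patient counts and rates, overall and serious, are also for reactions. The onset item in the same entry then asks for a summary ("the number of patients, the mean, median, maximum values) of days to onset of adverse events by PT"), and the same by primary survey item.

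Table 2.4.3, the reaction table for important identified risks, words the matching item as "summary of statistics of days to onset of adverse reactions (the number of patients, the mean, median, maximum values").

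For repeated PTs ("If there are events with same PT in one patient"), Tables 2.4.2 and 2.4.3 both send the reader to Table 2.4.1. The notes there rank serious above non-serious and send onset, outcome and days to outcome on to Section 10.2. For onset, Section 10.2 says that "the onset date of the event that occurred first should be used to identify the events to be aggregated". For days to outcome it takes the longest-lasting event of that PT. Neither of these two rules mentions causality.

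Section 2 defines summary statistics to include "standard deviation, the minimum value, the first quartile point, median value, the third quartile point, and the maximum value". The onset items of Tables 2.4.1 to 2.4.3 list only n, mean, median and maximum, while the days-to-outcome items in the same entries also list the minimum.

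**The concern.** By the definitions in Sections 2 and 10.2, reactions are the adverse events that remain once those assessed as not related are removed. Timing and course of the reactions, for infection, tuberculosis, malignancy and the other primary survey items, are what Table 2.4.2 adds to Table 2.4.1. If the onset item is programmed as worded, one row mixes two record sets: the counts come from reactions and the onset statistics from all adverse events.

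Even where the row is limited to patients with a reaction, the order of two steps matters. Filtering on causality and then keeping one record per PT can give a different onset or duration from keeping one record and then filtering. The SAP does not fix that order for Tables 2.4.2 and 2.4.3. According to Section 3.1, the results feed the survey report to the authority and the reassessment application, so the table should have one meaning.

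**Working it through.** There is no planned figure to reproduce. The check is a comparison of wording and a trace of the cross-references.

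1. **Onset item, three tables side by side.**
   - Table 2.4.1: objective on events, onset item on events. Consistent.
   - Table 2.4.2: objective on reactions, counts on reactions, onset item on events. Inconsistent.
   - Table 2.4.3: objective on reactions, counts on reactions, onset item on reactions. Consistent.

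   The onset phrase in Table 2.4.2 matches Table 2.4.1 word for word, which suggests that it was carried over. Table 2.4.3 shows that the authors do draw the distinction.

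2. **Repeated-PT chain.** The notes of Tables 2.4.2 and 2.4.3 lead to the notes of Table 2.4.1 and from there to Section 10.2.
   - Onset: first event of the PT; no causality condition.
   - Days to outcome: longest event of the PT; no causality condition.
   - Outcome: worst category in a fixed order, but the rule lists adverse events, adverse reactions and their serious subsets as separate aggregations, so it is already written per class.
   - Seriousness: serious over non-serious; no causality condition. The Section 10.2 definition of a serious adverse reaction also starts from adverse events and names only the seriousness criterion.

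3. **What each reading would print.** Take a hypothetical patient A with an unrelated episode on day 30 and a related episode of the same PT on day 300, and a patient B whose only event of that PT is unrelated. The reaction count in the row is 1 (patient A).
   - Reading 1, the objective governs and reactions are selected first: onset n = 1, value 300.
   - Reading 2, the row is limited to patients with a reaction but the first event is picked among all events: onset n = 1, value 30.
   - Reading 3, the onset item is taken literally: onset n = 2 (A and B) against a reaction count of 1, and A contributes 30.

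   The title, objective and counts of Table 2.4.2 favour reading 1. The onset item supports reading 3, and the silent repeated-PT rule permits reading 2. For Table 2.4.3 only readings 1 and 2 are in play.

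4. **Minimum.** The Section 2 definition and the quantitative-data row of Section 9.2 both include the minimum. The onset items of all three tables omit it, although each of those tables gives it for days to outcome.

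**The case against.** The best defence is that the objective sets the record set. Once the table is confined to reactions, the first record of a PT is the first reaction, and nothing assessed as not related can enter. The SAP also uses the word event loosely inside tables that hold only reactions: the notes of Tables 2.7, 2.13.1 and 2.17 do so, and Table 2.7 goes on to speak of the first-onset reaction. On that view the fault is one carried-over word in a descriptive column with no test or decision attached, and the counts and rates are correctly specified.

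Much of this stands. A reader might infer that unrelated events do supply the onset times in Table 2.4.2, that its onset column must equal that of Table 2.4.1, or that the reaction's outcome is drawn from unrelated episodes. The documents do not support these readings. The Section 10.2 onset rule is silent on causality and does not disregard it expressly, the table's title and objective point the other way, and the outcome rule treats reactions as their own class. Nor is the earliest onset lost: the patient list and the list of adverse events in 13.1 give days from start of administration and causality for each event, and Table 2.7 groups first-onset reactions by time window.

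The defence does not remove the contradiction. The analysis items are what the programmer implements, and here they name a different record set from the objective above them. Table 2.7 shows that the SAP can state the rule for reactions; Tables 2.4.2 and 2.4.3 do not.

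**Conclusion.** The point holds as an internal inconsistency in Table 2.4.2 and an unstated order of operations in Tables 2.4.2 and 2.4.3. It does not establish that unrelated events will appear in the reaction tables, only that the text allows it.

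The size cannot be given. It depends on how many events of the primary survey items are assessed as not related and on how many patients have both an unrelated and a related episode of one PT, and the SAP reports neither. Reading 3 would affect every row that has an unrelated event. Reading 2 would affect only patients with an earlier or longer unrelated episode of the same PT as their reaction. Counts and rates of reactions are outside the onset-wording problem, and no hypothesis test uses these columns. The correction should be made because the instruction is wrong as it stands and costs almost nothing to put right. The missing minimum is a minor reporting matter.

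**What to change.** - In the analysis items of Table 2.4.2, make the onset statistic refer to adverse reactions, as Table 2.4.3 does.
- In the notes of Tables 2.4.2 and 2.4.3, add one sentence: records are first restricted to adverse reactions in the safety analysis period, and the repeated-PT rules for seriousness, onset, outcome and days to outcome are then applied within that set.
- As a minor addition, include the minimum among the onset statistics in Tables 2.4.1 to 2.4.3, as is already done for days to outcome.

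The cost is a short SAP wording change and a causality filter placed before de-duplication in the table program. No new data are needed.
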